8.2 Evaluation after protocol treatment

	Investigations	Timing
History and Physical Exam including:	
 physical examination including, pulse, blood pressure, weight performance status 	Within 30 days following last treatment day
Hematology	
 CBC including haemoglobin, differential, platelet count 	Within 30 days following last treatment day
Biochemistry	
 AST (SGOT) and ALT (SGPT) alkaline phosphatase bilirubin albumin creatinine lipase (and amylase if abnormal lipase) fasting glucose K, Cl, Na, Ca 	Within 30 days following last treatment day
	
 TSH (T3, T4 if TSH abnormal) 	As clinically indicated
Radiology*	
 CT-scan of chest and upper abdomen 	Every 8 weeks
Other	
 ECG 	As clinically indicated

Investigations	
• lung function tests: FEV1, FVC, TLCO and blood gas at room atmosphere	As clinically indicated
Adverse Events	Patients must be evaluated for treatment related adverse events until resolution	

* Only for patients who have not yet discontinued the study treatment

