6.2 Early treatment termination

The investigator may terminate a patient's participation early in the event of:

- Tumour progression during treatment
- Toxicity requiring termination of study treatments
- Intercurrent illness
- Protocol violation
- Non-compliance (nivolumab)
- Administrative reasons
- Pregnancy

7 PRE-TREATMENT EVALUATION:

Investigations		Timing
History and Physical Exam including:	
 history including (occupational), smoking history physical examination including height, weight, pulse, blood pressure performance status (PS) 	Within 14 days of inclusion
Haematology	
 CBC including haemoglobin, differential, platelet count 	Within 14 days of inclusion
Biochemistry	
 AST (SGOT) and ALT (SGPT) alkaline phosphatase bilirubin albumin serum creatinine lipase fasting glucose K, Cl, Na, Mg, Ca, P LDH CRP TSH (T3, T4 if TSH abnormal) INR/APTT 	Within 14 days of inclusion
Immunovirology	
 Serology EBV, HCV/HBV, CMV, Toxoplasmosis - TPHA-VDRL, HHV-8 Quantiferon 	Before inclusion
	
 CD4/CD8 cell counts HIV viral load (VL) HCV/HBV VL, HHV-8 VL in the case of co-infection EBV VL, CMV VL 	Within 28 days of inclusion ; those VL will be monitored further in case of positivity
Radiology ¹	
 baseline CT brain, chest and abdomen (with iodine injection) (Wang 2004) baseline PET-CT : highly recommended (but optional) (Ceresoli 2006b, von Schulthess 2006, Francis 2007) 	Within 28 days of inclusion
	
 other baseline imaging (e.g. bone scan,...) 	Required, within 28 days of inclusion, only if suspicious signs/symptoms are present
Correlatives	
 tumour tissue for assessment of PD-L1 status 	From initial diagnosis block

	
 whole blood, serum, plasma for correlatives 	Prior to cycle 1, day 1 dosing
Other Investigations	
 ECG 	Within 14 days of inclusion
	
 pregnancy test if applicable 	Within 24hrs of first drug administration
Adverse Event	Baseline adverse event evaluation (to document residual adverse event from previous therapy and baseline symptoms)	Within 14 days of inclusion
Quality of Life	LCSS questionnaire	Within 14 days of inclusion

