8 EVALUATION DURING AND AFTER PROTOCOL TREATMENT

8.1 Evaluation during Protocol Treatment

	Investigations	Timing
History and Physical Exam including:	
 physical examination including, pulse, blood pressure, weight performance status 	Prior to each infusion until off protocol therapy
Hematology	
 CBC including hemoglobin, differential, platelet count 	Prior to each infusion until off protocol therapy
Biochemistry	
 AST (SGOT) and ALT (SGPT) alkaline phosphatase, gamma GT Bilirubin, LDH albumin creatinine, urea lipase (and amylase if abnormal lipase) fasting glucose K, Cl, Na, Ca, Mg²⁺ Urinary test 	Prior to each infusion until off protocol therapy
	
 TSH (T3, T4 if TSH abnormal) Antinuclear antibody and in case of positivity anti-ENA and anti-DNA; anti-thyroperoxydase, anti-thyroglobulin 	Every 6 weeks, until off protocol therapy
Immunolovirology (2)	
 Hbs antigen, HCV/HBV VL, HHV-8 VL in the case of co-infection EBV VL, CMV VL, 	Cycle 2, 3, 9, 15, 27, 51, end of treatment and in case of immune related adverse event. Every 3 cycles for Hbs antigen, HCV/HBV VL

Immunolovirology (1)	
 CD4/CD8 cell counts HIV viral load (VL) 	Prior to each infusion until off protocol therapy
Radiology*	
 CT-scan of chest and upper abdomen Other imaging used for baseline tumoral assessment 	Every 8 weeks from randomization (CTs schedule must be maintained regardless of treatment delays)
Other Investigations	
 ECG 	As clinically indicated
	
 lung function tests: FEV1, FVC, TLCO and blood gas at room atmosphere 	Only if pulmonary symptoms or suspicion of pneumonitis
	
 pregnancy test if applicable 	Every 3 cycles ± 1 weeks
Correlatives	
 whole blood, serum, plasma 	Cycle 2, 3, 9, 15, 27, 51, end of treatment and in case of immune related adverse event.
Adverse Events	patients must be evaluated at each visit for adverse events according to CTCAE v4	
Quality of Life	
 LCSS questionnaire 	Cycle 2, 3, 5, 7, 9

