* Radiology assessments must be kept to schedule irrespective of any delays in a treatment cycle. If the schedule cannot be kept all attempts must be made to undertake the required imaging as soon as possible. Thereafter, patients must be put back on original imaging schedule.

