10 TREATMENT BEYOND DISEASE PROGRESSION

Accumulating evidence indicates a minority of subjects treated with immunotherapy may have clinical benefits despite initial evidence of PD.

Subjects treated with Investigational Treatment will be permitted to continue treatment beyond initial RECIST 1.1 defined PD - at 8 weeks CT scan assessment - if they meet all of the following criteria:

1. Investigator-assessed clinical benefit, and subjects do not have rapid disease progression
2. Continue to meet all other study protocol eligibility criteria
3. Good tolerance of study drug
4. Stable performance status

After the 8 weeks CT-scan, a new CT-scan assessment should be performed within 4 weeks \pm 1 week from original PD scan to determine whether there has been a decrease in the tumour size or disease stabilization, or alternatively continued PD, which would terminate the trial treatment.

For the subjects who continue IP beyond progression, further progression is defined as an additional 10% increase in tumour volume from time of initial PD. This possibility has been introduced to take into account the pseudo-tumoral progressions sometimes observed under immune check-point inhibitors treatment. In case of the second evaluation would confirm disease progression and the clinical benefit no longer confirmed, the date of progression will be set at the date of the first CT-scan showing mRECIST criteria of progression (*Wolchok 2009*).

In case of disease control, the experimental treatment will be given until disease progression (tumor assessment every 8 weeks \pm 1 week).

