12.4 Discontinuation of treatment

Treatment with nivolumab should be permanently discontinued for any of the following:

- Any Grade ≥ 3 drug-related pneumonitis or interstitial lung disease
- Grade 4 colitis or diarrhea
- Grade ≥ 3 elevation in AST, ALT or total bilirubin
- Grade 4 creatinine elevation
- Grade 4 rash, grade 4 pruritus
- Grade 2 or 3 immune-related adverse reactions that persist despite treatment modifications or for inability to reduce corticosteroid dose to 10 mg prednisone or equivalent per day.
- Dosing delays lasting > 6 weeks from the previous dose that occur for non-drug-related reasons may be allowed if approved by IFCT. Prior to re-initiating treatment in a subject with a dosing delay lasting > 6 weeks, IFCT must be consulted. Tumor assessments should continue as per protocol even if dosing is delayed. Periodic study visits to assess safety and laboratory studies should also continue or more frequently if clinically indicated during such dosing delays.
- Any adverse event, laboratory abnormality, or intercurrent illness which, in the judgment of the Investigator, presents a substantial clinical risk to the subject with continued nivolumab dosing.

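### The footnote to the post-treatment CT row in Protocol 8.2 excludes every patient off treatment, so no readable text explicitly schedules scans after a stop without progression

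*Protocol*

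**What the plan says.** Section 8.2 of the Protocol tabulates what is done once protocol treatment has ended. Its examination, haematology and main biochemistry rows are timed from the last treatment day. The radiology row asks for a CT of chest and upper abdomen every 8 weeks and carries an asterisk, explained under the table as "Only for patients who have not yet discontinued the study treatment".

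The other readable text on imaging is as follows:

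- **Section 8.1 (during treatment), radiology row:** CT every 8 weeks, with the note "CTs schedule must be maintained regardless of treatment delays". Its footnote adds "Radiology assessments must be kept to schedule irrespective of any delays in a treatment cycle". Several neighbouring rows end with "Prior to each infusion until off protocol therapy"; the CT row does not.
- **Section 10:** for patients with disease control, "the experimental treatment will be given until disease progression (tumor assessment every 8 weeks", with a window of one week either side.
- **Section 12.4:** "Tumor assessments should continue as per protocol even if dosing is delayed".
- **Section 3:** follow-up after stopping is described for patients whose tumour has progressed, and covers survival and toxicity only.

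Permanent stops for other reasons are foreseen. Section 6.2 lists "Toxicity requiring termination of study treatments", along with intercurrent illness, non-compliance, administrative reasons and pregnancy. Section 12.4 opens with "Treatment with nivolumab should be permanently discontinued for any of the following" and gives toxicity criteria unrelated to tumour status.

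Section 13.4.2 measures PFS from inclusion to documented progression or death. Patients with neither are censored at their last evaluable tumour assessment. Duration of response is also a secondary endpoint (section 2.2).

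**The concern.** A patient being evaluated after protocol treatment has, by definition, discontinued it. The footnote therefore removes from the CT row everyone the table is about. The patient at issue stops nivolumab permanently, for toxicity for example, with the disease still controlled.

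If sites follow the footnote, that patient has no scheduled scans after the stop. One of three things then happens to the PFS record:

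1. Progression is found on a scan taken for another reason, usually symptoms, at an unplanned time.
2. Progression is never documented and the event is dated at death, which is later.
3. The patient is alive at the analysis and is censored at the last on-treatment scan.

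Which of these applies depends on the patient's later course, so the censoring may be informative. Duration of response relies on the same scans. Scans not taken cannot be recovered by any analysis rule. The row and its footnote can also be read in opposite ways, so practice may differ across the twenty planned centres.

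**Working it through.** **1. Does any readable text schedule the scans?** The question is who is imaged after a permanent stop without progression.

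| Place | Situation covered | Covers this patient? |
|---|---|---|
| 8.2, CT row | after treatment | yes by the heading, no by the footnote |
| 8.1, CT row and footnote | during treatment, including delays | not explicitly |
| 10 | treatment continuing | no |
| 12.4, tumour assessments | dosing delayed | no |
| 3 | stopped for progression; survival and toxicity | no |

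A delay is not a permanent stop: the protocol handles them separately, in 12.2 and 12.4. The only line written for patients off treatment is the one the footnote cancels.

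**2. How far can the PFS curve move?** Let n be the number analysed, k the number who stop without progression and are not scanned, and s the number of the other n − k patients who are event-free at time t. Assume none of those others is censored before t.

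- With complete imaging, S(t) lies between s/n (all k have had an event by t) and (s + k)/n (none has).
- In Kaplan-Meier estimation each patient starts with weight 1/n, and a censored patient's weight passes to those still at risk. The weight that can be passed on is at most k/n, so with the k patients censored or dated later S(t) also lies between s/n and (s + k)/n.
- The two values therefore differ by at most k/n.

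| | n = 28 (eligible) | n = 30 (ITT sensitivity analysis) |
|---|---|---|
| k = 1 | 1/28 = 3.6 points | 1/30 = 3.3 points |
| k = 2 | 2/28 = 7.1 points | 2/30 = 6.7 points |

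Dating at death moves an event later, so it can only raise the curve. Censoring can move it either way.

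**3. Illustration for the median (assumed inputs, not in the protocol).** Take exponential PFS with a median of 3 months and 10% to 30% permanent stops by 6 months in the absence of progression. About 2 to 6 of 28 patients would then stop before progressing. If all are censored at the stop, the Kaplan-Meier median stays at about 3.0 months. With complete imaging it would be 3.0 months if stopping leaves the hazard unchanged, and 2.8 to 2.9 months if the hazard doubles after the stop.

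**4. Primary endpoint.** Section 13.2 stops for futility at 4 or fewer of 14 controlled and declares success at 13 or more of 28. The exact success probability at control rate p is the sum, over x = 5 to 14, of P(X = x) × P(Y ≥ 13 − x), with X and Y both binomial(14, p).

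- At p = 0.30 this gives 0.047, within the stated one-sided 5%.
- At p = 0.57 it gives 0.896, close to the intended 90% (printed as β, read here as power).

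Section 13.4.1 counts unevaluable patients as failures, so missing scans cannot inflate the false-positive rate; they can only cost power. If 5% of controlled patients stopped before week 8 and went unscanned, p would be 0.57 × 0.95 = 0.5415 and power 0.831. At 10%, p would be 0.513 and power 0.745. Nothing in the protocol supports either rate, and the conclusion does not rest on them.

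**5. Scans at stake.** 52/8 = 6.5, so 6 scheduled CTs per progression-free year off treatment. Section 15.6 keeps the study open for one year after the last patient's last treatment.

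**The case against.** The strongest reply is that the footnote is a drafting slip whose intent is visible. An 8-weekly CT in a post-treatment table makes sense only if off-treatment imaging was meant. The 8.1 CT row is counted from entry rather than from infusions and lacks the off-therapy limit of its neighbours, which points the same way. This is plausible, and the footnote may have been meant for patients who have not yet progressed. But the protocol does not say so. The reading relies on silence in a table headed for the treatment period, against an express footnote saying the opposite.

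Second, the study-design figure in section 3 cannot be read here and might show such imaging. That is a fair limit, and the point is confined to readable text. If the figure does schedule these scans, the footnote contradicts it as well.

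Third, little depends on it. PFS and duration of response are secondary, no PFS test is described, the frequency of such stops is unknown, and the illustrated median barely moves. All of this stands and limits the severity. The k/n figure is also conditional: if other patients are censored earlier, one patient can carry more than 1/n of the curve.

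Fourth, section 13.4.2 does define how these patients are analysed. That is true, but a censoring rule does not replace the missing scans or make the censoring non-informative.

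**Conclusion.** The concern holds and should be fixed. The footnote contradicts the heading of its own table. Followed as written, it ends scheduled imaging for patients who stop permanently without progression, a group the protocol expects. No other readable passage explicitly restores it.

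The size is not known, because the protocol gives no rate of such stops. What can be said is a bound of 3.6 percentage points on the PFS curve per affected patient with 28 analysed (3.3 with 30), provided the other patients are uncensored up to that time. A large shift in median PFS is not claimed. The effect falls on two secondary, estimated endpoints. The 8-week primary endpoint is reached only through stops before week 8, and then conservatively. Confidence is high on the contradiction; the amount of bias remains open.

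**What to change.** Reconcile the 8.2 footnote with its table heading and with the PFS definition in 13.4.2. Whether a patient has the 8-weekly CT already named in that row should depend on absence of documented progression, not on treatment status. In the same line, the sponsor should state whether this still holds once another anti-tumour therapy starts. If the section 3 figure shows a follow-up schedule, it should be checked against the new wording.

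The change is one line. The price is extra CTs for the patients who stop without progression, about 6 per patient per progression-free year off treatment, on a schedule the table already contains. It needs to be in place before such patients leave treatment, since it cannot be repaired at analysis.

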9 STUDY TREATMENT

The study treatments are explained in table 1.

Table 1.

Active substance	Nivolumab
Commercial Name	Opdivo [®]
Pharmaceutical form	Concentrate for solution for infusion
Dosage	10 mg/mL
Posology	3mg/kg
Storage	Store in refrigerator (2°C - 8°C) in its original package in order to protect from light
Laboratory	BMS

The treatment has to begin within 15 days following inclusion.

These treatments will be labeled according to the regulation. These treatments will be administered until progression or limiting toxicities.

Nivolumab has a concentration of 10mg/mL and is provided in a 10mL vial.

Storage Conditions & Handling:

- Store at 2-8°C (36-46°F), protect from light, freezing, and shaking.
- If any temperature excursions are encountered during storage, please report these to IFCT for assessment via the Temperature Excursion Response Form.
- As with all injectable drugs, care should be taken when handling and preparing nivolumab. Whenever possible, nivolumab should be prepared in a laminar flow hood or safety cabinet using standard precautions for the safe handling of intravenous agents applying aseptic technique.

- Partially used vials should be disposed at the site following procedures for the disposal of anticancer drugs.

Use Time/Stability: Please refer to the appropriate section of the current Investigator Brochure or Addendum. Due to parameters surrounding the use time of nivolumab, the time of preparation should be noted in the Pharmacy Source documents [accountability logs] or in study files as required for investigator sponsored research [FDA and GCP]

The administration of nivolumab infusion must be completed within 24 hours of preparation. If not used immediately, the infusion solution may be stored up to 20 hours in a refrigerator at under refrigeration conditions (2° - 8°C, 36° - 46°F) and used within 24 hours, and a maximum of 4 hours of the total 24 hours can be at room temperature (20° - 25°C, 68° - 77°F) and under room light. The maximum 4-hour period under room temperature and room light conditions for undiluted and diluted solutions of nivolumab injection in the IV bag includes the product administration period.

Preparation and Administration:

1. Visually inspect the drug product solution for particulate matter and discoloration prior to administration. Discard if solution is cloudy, if there is pronounced discoloration (solution may have a pale-yellow color), or if there is foreign particulate matter other than a few translucent-to-white, amorphous particles. **Note:** *Mix by gently inverting several times. Do not shake.*
2. Aseptically withdraw the required volume of nivolumab solution into a syringe, and dispense into an IV bag. If multiple vials are needed for a subject, it is important to use a separate sterile syringe and needle for each vial to prevent problems such as dulling of needle tip, stopper coring, repeated friction of plunger against syringe barrel wall. **Do not** enter into each vial more than once. **Do not** administer study drug as an IV push or bolus injection
3. Add the appropriate volume of 0.9% Sodium Chloride Injection solution or 5% Dextrose Injection solution. *It is acceptable to add nivolumab solution from the vials into an appropriate pre-filled bag of diluent.*
4. **Note:** *Nivolumab infusion concentration must be at or above the minimum allowable concentration of 0.35 mg/mL [IBV15 Addendum Section 3.2.2]*
5. **Note:** *It is not recommended that so-called “channel” or tube systems are used to transport prepared infusions of nivolumab.*
6. Attach the IV bag containing the nivolumab solution to the infusion set and filter.

7. At the end of the infusion period, flush the line with a sufficient quantity of approved diluents.

10 TREATMENT BEYOND DISEASE PROGRESSION

Accumulating evidence indicates a minority of subjects treated with immunotherapy may have clinical benefits despite initial evidence of PD.

Subjects treated with Investigational Treatment will be permitted to continue treatment beyond initial RECIST 1.1 defined PD - at 8 weeks CT scan assessment - if they meet all of the following criteria:

1. Investigator-assessed clinical benefit, and subjects do not have rapid disease progression
2. Continue to meet all other study protocol eligibility criteria
3. Good tolerance of study drug
4. Stable performance status

After the 8 weeks CT-scan, a new CT-scan assessment should be performed within 4 weeks \pm 1 week from original PD scan to determine whether there has been a decrease in the tumour size or disease stabilization, or alternatively continued PD, which would terminate the trial treatment.

For the subjects who continue IP beyond progression, further progression is defined as an additional 10% increase in tumour volume from time of initial PD. This possibility has been introduced to take into account the pseudo-tumoral progressions sometimes observed under immune check-point inhibitors treatment. In case of the second evaluation would confirm disease progression and the clinical benefit no longer confirmed, the date of progression will be set at the date of the first CT-scan showing mRECIST criteria of progression (*Wolchok 2009*).

In case of disease control, the experimental treatment will be given until disease progression (tumor assessment every 8 weeks \pm 1 week).

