4 ELIGIBILITY

4.1 Inclusion Criteria

1. Age ≥ 18 years old
2. HIV1 or HIV2, regardless of CD4 cell count
3. HIV Viral load <200 copies/mL
4. Proven histologically and/or cytologically, stage IIIB-IV or metastatic relapse post-surgery non-small cell lung cancer (NSCLC)
5. Disease recurrence or progression during/after at least one prior platinum doublet-based chemotherapy regimen for advanced or metastatic disease
6. Measurable disease by Computed tomography (CT)/Magnetic resonance imaging (MRI) per RECIST 1.1 criteria
7. Performance status (PS) 0, 1 or 2
8. Written informed consent
9. Patients must have adequate organ function: creatinine clearance > 40 mL/min (Cockcroft, MDRD or CKD-Epi formula or 24h Urine Calculate creatinine clearance from a 24h urine collection), neutrophiles count > 1500/mm³; platelets > 100 000/mm³ ; hemoglobine > 9 g/dL; hepatic enzymes < 3N with total bilirubin ≤ 1.5 × ULN (upper limit of normal) except subjects with documented Gilbert's syndrome (≤ 5 × ULN) or liver metastasis, who must have a baseline total bilirubin ≤ 3.0 mg/dL
10. Patients must receive appropriate care and treatment for HIV infection including ART when clinically indicated and subjects should be under the care of a physician experienced in HIV management. In case of recent introduction of cART and CD4 levels <50 cells/ml, inclusion will be possible provided subjects had at least 4 weeks of

treatment prior to inclusion, to avoid clinical type IRIS (immune inflammatory syndrome reconstitution). All antiretroviral treatments are allowed.

11. Females of childbearing potential who are sexually active with a nonsterilized male partner must use a highly effective method of contraception for 28 days prior to the first dose of investigational product, and must agree to continue using such precautions for 6 months after the final dose of investigational product; cessation of contraception after this point should be discussed with the referent physician. Periodic abstinence, the rhythm method, and the withdrawal method are not acceptable methods of contraception. They must also refrain from egg cell donation for 6 months after the final dose of investigational product. Men receiving nivolumab and who are sexually active with women of childbearing potential will be instructed to adhere to contraception (appendix I) for a period of 31 weeks after the last dose of nivolumab.

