13.4.2 Secondary endpoints

- Progression-free Survival (PFS) and Overall Survival (OS)

PFS is defined as the time between the date of inclusion and the first date of documented progression or death due to any cause, whichever occurs first. Subjects who die without a reported progression will be considered to have progressed on the date of their death. Subjects who did not progress or die will be censored on the date of their last evaluable tumor assessment.

The duration of overall survival is defined as the time elapsed between the date of inclusion and death. Subjects who did not die will be censored on the last date a subject was known to be alive.

The median survival, 95% confidence intervals and an estimation of progression-free survival (PFS) and overall survival according to the Kaplan-Meier Method will be calculated using standard methods

This analysis will be performed on all eligible patients.

PFS and OS will be also conducted on all patients (ITT analysis) as a sensitivity analysis.

- Tolerance

The toxicity analysis will be performed on the safety population.

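### Section 10's only explicit rule for further progression is fixed to the size at initial PD, and it is not reconciled with the section's closing sentence, its other yardsticks or the PFS definition.

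*Protocol*

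**What the plan says.** Protocol section 10 covers patients who are "permitted to continue treatment beyond initial RECIST 1.1 defined PD - at 8 weeks CT scan assessment". They have a further CT 4 weeks ± 1 week later, "to determine whether there has been a decrease in the tumour size or disease stabilization, or alternatively continued PD, which would terminate the trial treatment".

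The rule for what counts next opens with "For the subjects who continue IP beyond progression" and states that "further progression is defined as an additional 10% increase in tumour volume from time of initial PD". The sentence after it gives pseudo-progression as the reason for allowing continuation.

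Two further sentences matter:

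- If the second evaluation confirms progression and clinical benefit is no longer confirmed, "the date of progression will be set at the date of the first CT-scan showing mRECIST criteria of progression".
- "In case of disease control, the experimental treatment will be given until disease progression", with assessment every 8 weeks. No criterion is attached.

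Elsewhere, section 4.1 (criterion 6) requires "Measurable disease by Computed tomography (CT)/Magnetic resonance imaging (MRI) per RECIST 1.1 criteria". Section 13.4.2 defines the PFS event as "the first date of documented progression or death due to any cause". Section 2.2 lists duration of response as a secondary endpoint. New lesions are not mentioned anywhere in the protocol.

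**The concern.** In a true pseudo-progression the week-8 size is the inflated one. A rule that measures all later growth from that size lets more regrowth go uncounted the more a patient has shrunk. The explicit definition has no time limit and covers all patients continued beyond progression, including those the provision was written for.

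The surrounding text does not settle whether this rule governs the whole later course or only the second scan. It also leaves open which yardstick documents a later progression for PFS. Two investigators, or an investigator and the trial statistician, could date the same patient's progression at different scans, and both could cite the protocol. The trial is open-label and single-arm with 30 patients. A few such dates can move the PFS and duration-of-response estimates, and there is no control arm in which the same choice would be made.

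**Working it through.** **1. The design figures, to see what is in play.** Section 13.2 gives futility at ≤4/14 and success at ≥13/28, with rates of 30% and 57%. By exact binomial, the 13/28 rule alone has one-sided alpha 0.0491 and power 0.906. With the futility stop these are 0.0469 and 0.896. This agrees with the plan (its 90% is labelled β and is read here as power). Sections 13.2 and 13.4.1 assess control at 8 weeks, before any rule on further progression operates, so this point does not touch these figures.

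**2. What the literal rule implies.** The protocol gives no tumour sizes, so these are assumptions: size P at initial PD and smallest later size S, in mm. The text says volume, whereas RECIST works on diameters, so both readings are shown.

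- On diameters: threshold = 1.10 × P.
- On the volume of a sphere: threshold in diameter = P × 1.10^(1/3) = P × 1.0323.
- Regrowth needed = threshold / S − 1.

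| P | S | Threshold, diameters | Regrowth from S | Threshold, volume reading | Regrowth from S |
|---|---|---|---|---|---|
| 120 | 120 | 132 | +10% | 123.9 | +3% |
| 120 | 100 | 132 | +32% | 123.9 | +24% |
| 120 | 80 | 132 | +65% | 123.9 | +55% |
| 120 | 60 | 132 | +120% | 123.9 | +106% |
| 130 | 50 | 143 | +186% | 134.2 | +168% |
| 150 | 30 | 165 | +450% | 154.8 | +416% |

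For the main example: 1.10 × 120 = 132 and 132/60 = 2.20; 120 × 1.0323 = 123.9 and 123.9/60 = 2.06. The same rule is tight for a patient who merely stabilises and very loose for one who responds.

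For scale, assume a cut-off of +20% from the smallest sum (the protocol prints none). Regrowth would then count at 1.2 × 60 = 72 mm, or at 1.2 × 80 = 96 mm when S is 80.

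**3. The sentences side by side, for a patient with PD at week 8 and control at the second scan.**

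| Question | Text | Answer given |
|---|---|---|
| When does progression next count? | Section 10, 10% rule | At +10% volume from initial PD |
| Same | Section 10, last sentence | At disease progression, criterion and reference not stated |
| Which yardstick? | Section 10 | RECIST 1.1 for initial PD, tumour volume for further progression, mRECIST for the date |
| Is the week-8 PD a PFS event? | Section 13.4.2 | Yes, as the first documented progression |
| Same | Section 10 | Back-dating is provided only if the second evaluation confirms PD; nothing is said otherwise |

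**4. Why the endpoint repair cannot simply be the smallest sum on study.** That sum includes baseline. Assume baseline 100 mm, 120 mm at week 8, still 120 mm at the second scan, and the +20% cut-off. Then 120/100 = 1.20, so the patient would be scored as progressing at once, although section 10 has a category for stabilisation at that scan. The reference has to start at the week-8 scan.

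**The case against.** A reader might infer that neither regrowth nor a new lesion ever counts as progression in these patients. The text does not support that.

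- The 10% sentence stands between the one ordering the second scan and the one on its confirmation of PD, so it can be read as the test for that scan alone. Patients with control at that scan have their own closing sentence, which carries no 10% rule and can be read as ordinary RECIST 1.1 progression.
- A new lesion may enter through total tumour volume, or be called continued PD. Section 10 also cites an outside source for its progression criteria, and how that source treats new lesions cannot be seen here.

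A reader might also infer that PFS is biased long. Section 13.4.2 read as written puts the event at week 8, and the one dating rule in section 10 moves the date back, not forward. Lengthening would require that an unconfirmed week-8 PD is set aside for PFS, which the protocol does not say. A definition of duration of response may properly stand in the SAP.

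Nor does the text establish that treatment would run on through relapse. Continuation requires clinical benefit without rapid progression, good tolerance and stable performance status, and section 6.2 lets the investigator stop for tumour progression.

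All of this stands, and so does the fact that every size above is assumed. What remains is that the sentence with a criterion and the sentence without one can both be applied to the same patients, and nothing says which prevails.

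**Conclusion.** The definition is incomplete and unreconciled. The only explicit criterion for further progression is fixed to initial PD, has no smallest-size reference and does not say how new lesions are handled. On the literal reading, with the sizes assumed above, a patient who shrinks from 120 mm to 60 mm must roughly double, to about 124 to 132 mm, before it is met. Across the cases with shrinkage to 80 mm or less, the regrowth needed runs from +55% to +450%.

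These figures show what the literal rule permits; they do not estimate bias. A delay in days would need a growth rate that the protocol does not give, and the number of patients affected is unknown (section 10 itself expects only a minority to benefit after initial PD).

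The reach is limited to the later progression date, any duration of response and the time on treatment of patients continued beyond week-8 PD. The primary 8-week decision at 4/14 and 13/28 does not change.

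**What to change.** **Endpoints (PFS and duration of response).** State whether a week-8 PD that the second scan does not confirm is an event. If it is, section 13.4.2 can stand and needs only a cross-reference to section 10. If it is not, state that progression after a controlled second scan is scored on the RECIST measurement scale, from the smallest sum recorded from the week-8 scan onward, counting lesions that are new since that scan, and that the fixed initial-PD reference is not used. Name one criterion in place of the three labels.

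**Treatment.** The 10% rule and the closing sentence of section 10, including the handling of new lesions, must be reconciled. That choice is the sponsor's, and no clinical rule is proposed here.

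**Cost.** One or two sentences for the endpoints and one clarification in section 10. The 8-weekly CTs in section 8.1 and the second scan in section 10 already supply the measurements, so no scans are added and the sample size does not change. As the trial is open-label, the wording should be fixed before later progression dates are analysed.
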